- Had unprotected sexual intercourse within 30 days before study entry and who do not agree to use a highly effective method of contraception (e.g., total abstinence, an intrauterine device [IUD], a double-barrier method [such as condom plus diaphragm with spermicide], an oral contraceptive, or have a vasectomized partner with confirmed azoospermia) throughout the entire study period or for 70 days after the last dosing.
- Are currently abstinent, and do not agree to use a double-barrier method (condom plus diaphragm with spermicide) during the study period or for 70 days after the last dosing.
- Are using oral contraceptives but are not on a stable dose of the same oral contraceptives for at least 4 weeks before study treatment, or who do not agree to use the same oral contraceptives during the study or for 70 days after the last dosing.
- All women will be considered to be of childbearing potential unless they are postmenopausal [amenorrheic for at least 12 consecutive months, in the appropriate age group, and without other known or suspected cause] or have been sterilized surgically [i.e., either of bilateral tubal ligation, total hysterectomy, or bilateral oophorectomy was performed at least 1 month before study treatment].

32. Men who have not had a successful vasectomy (without confirmed azoospermia) and their female partners do not meet any of the criteria above (however, study entry is allowed if the female partner is not of childbearing potential or practicing highly effective contraception throughout the study period or for 70 days after the last dosing). No sperm donation is allowed during the study period or for 70 days after the last dosing.

33. Scheduled for surgery during the study

34. Currently enrolled in another clinical study, or used any investigational drug or device within 28 days (or $5\times$ the half-life, whichever is longer) before informed consent

- 35. Has been treated with E6011 or any unapproved biologics for RA
- 36. Use of a psychotropic agent as recreational purpose other than therapeutic purpose
- 37. Any history of a medical condition or a concomitant medical condition that in the opinion of the investigator or subinvestigator would compromise the subject's ability to safely complete the study

Study Treatments

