9 INVESTIGATIONAL PLAN

9.1 Overall Study Design and Plan

This study is a multicenter, randomized, double-blind, placebo-controlled, parallel-group comparison study. The following 4 treatment groups are selected for the study: E6011 100 mg, 200 mg, 400 mg, and placebo. In the E6011 100 mg, 200 mg, and placebo groups, subjects will receive the study treatment (100 mg, 200 mg, or placebo, respectively) at Weeks 0, 1, 2, and then every 2 weeks. In the E6011 400 mg group, subjects will receive 400 mg at Weeks 0, 1, 2, 4, 6, 8, 10 and then 200 mg every 2 weeks.

The study consists of Screening, Observation, Treatment, Extension, and Follow-up Phases.

Screening assessments will be performed within 42 days prior to the study treatment, and subjects with the certain eligibility confirmed in the Observation Phase will be allocated to any of the E6011 100 mg, 200 mg, 400 mg, or placebo groups at a 1:2:2:2 ratio through dynamic allocation using the following factors: C-reactive protein (CRP) level at the Screening Phase, disease duration and history of biologics treatment.

In the Treatment Phase (24 weeks), subjects will receive either E6011 or placebo at Weeks 0, 1, 2, and every 2 weeks until Week 22 in a double-blind manner.

Subjects who complete evaluations at Week 24 of the Treatment Phase will enter the Extension Phase. The Extension Phase is up to 104 weeks after the start of the study treatment, and subjects will receive an open-label E6011 200 mg every 2 weeks until Week 102. If the investigator or subinvestigator judges that the response to treatment is insufficient in the Extension Phase, administration of E6011 400 mg every 2 weeks will also be allowed (reduction of the dose back to 200 mg after an increase to 400 mg will also be allowed).

If subjects complete or discontinue the study, a follow-up visit should be conducted 28 days after the completion or discontinuation of the study, and a follow-up visit or telephone interview should be conducted 70 days after the last dosing.

An overview of the study design is presented in Figure 1.

[figure not shown]

Figure 1 Study Design

*: If the investigator or subinvestigator judges that response to treatment is insufficient during the Extension Phase, administration of E6011 400 mg every 2 weeks will also be allowed.

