Since the result from Study 103 suggested the efficacy of E6011 in its 12-week treatment period, the primary endpoint of this study is determined to be ACR20 response rate at Week 12. E6011 is expected to have an inhibitory effect against the structural damage of joints through inhibition of bone absorption in RA. Therefore, modified Total Sharp Score (mTSS), a measure for joint destruction progression, is also evaluated in this study. “The Guideline for the clinical evaluation of antirheumatic drugs” and clinical study data of

similar drugs to E6011 indicate that at least 24 weeks is required for mTSS evaluation; thus, the double-blind part of this study is designed to be 24 weeks.

Subjects who complete the double-blind part for 24 weeks will be able to proceed to the Extension Phase, where E6011 200 mg may be administered every 2 weeks up to Week 104 in an open-label manner. Our target is patients who inadequately respond to MTX, a standard therapeutic agent for RA. Therefore, we consider that the study design where subjects can continue E6011 treatment is useful from the perspective of patient benefit.

Furthermore, if the subjects insufficiently respond to the treatment in the Extension Phase, the design also allows for administration of E6011 400 mg every 2 weeks

The Follow-up Phase was set to be 70 days after the last dose of the study drug, which is approximately 5 times of the longest half-life of E6011 in the previous clinical data.

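### Exclusion 31 lets in one kind of subject it is meant to keep out: a sexually active woman, on no oral contraceptive and with no unprotected intercourse in 30 days, who declines highly effective contraception

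*Protocol*

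**What the plan says.** Exclusion 31 appears in the Synopsis and again in Section 9.3.2, with the same wording on this point. It has four bullets.

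- **Bullet 1** excludes when two joined conditions are both met: "Had unprotected sexual intercourse within 30 days before study entry and who do not agree to use a highly effective method of contraception". Its examples of acceptable methods include "a double-barrier method [such as condom plus diaphragm with spermicide" but not condoms alone.
- **Bullet 2** excludes a currently abstinent woman who will not agree to a double-barrier method.
- **Bullet 3** excludes an oral-contraceptive user who is not on a stable dose or will not agree to stay on the same product.
- **Bullet 4** excludes nobody. It defines the population: "All women will be considered to be of childbearing potential unless they are postmenopausal" or surgically sterilised.

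Exclusion 32 covers men without a successful vasectomy where "their female partners do not meet any of the criteria above". It allows entry if the partner is not of childbearing potential or is "practicing highly effective contraception throughout the study period or for 70 days after the last dosing". It closes with a ban: "No sperm donation is allowed during the study period or for 70 days after the last dosing".

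**The concern.** The criterion exists to prevent pregnancy during exposure to E6011. Because bullet 1 joins recent unprotected intercourse and refusal with *and*, refusal alone does not exclude. The result is inconsistent: an abstinent woman who refuses a double-barrier method is excluded, while a sexually active woman who refuses every highly effective method may be admitted.

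The protocol's other safeguards detect or respond to pregnancy; they do not prevent it. Exclusion 30 removes women who are already pregnant or breastfeeding. After dosing starts, Section 9.5.1.5.7 schedules pregnancy tests at Weeks 12, 24, 52, 76 and 104 and at discontinuation, so up to 52 − 24 = 28 weeks can pass between scheduled tests while the drug is given every 2 weeks. Sections 9.3.3 and 9.5.4.2 require withdrawal and reporting once a pregnancy has occurred.

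**Working it through.** There is no planned figure to reproduce; the check is of the logic of the text.

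**Exclusion 31.** Take a woman of childbearing potential who declines every highly effective method. The bullets turn on three factors:

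- unprotected intercourse in the past 30 days: yes or no
- currently abstinent: yes or no
- oral contraceptive: none, unstable dose or stable dose

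This gives 2 × 2 × 3 = 12 profiles. Recent intercourse and current abstinence can both be true, for example in a woman abstinent for the last two weeks, so no profile is dropped as impossible.

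| Unprotected intercourse in 30 days | Currently abstinent | Oral contraceptive | Profiles | Caught by |
|---|---|---|---|---|
| Yes | Either | Any | 1 × 2 × 3 = 6 | Bullet 1 |
| No | Yes | Any | 1 × 1 × 3 = 3 | Bullet 2 |
| No | No | Unstable or stable | 1 × 1 × 2 = 2 | Bullet 3 |
| No | No | None | 1 | No bullet |

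Caught: 6 + 3 + 2 = 11 of 12. Not caught: 1. These are logical cases, not proportions of subjects.

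**Who the missed woman is.** *Unprotected* is not defined, so there is a range:

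- If it means no method at all, the gap includes women relying on condoms alone.
- If it means not covered by a highly effective method, the condom-only woman is caught by bullet 1. The gap shrinks to women already using such a method, for example an intrauterine device, who will not commit to continuing it.

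The gap exists on either reading; only its width changes.

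**Exclusion 32 and the word *or*.** Exclusions 31 and 32 link the study period and the 70 days after the last dose with *or* five times. Four of these sit under a negation or a ban (bullets 1 to 3 of 31, and sperm donation), where *or* naturally covers both periods. The fifth, the exemption in 32, is a permission. Writing S for cover during the study period and P for cover during the 70 days:

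| S | P | Entry with *or* | Entry with *and* |
|---|---|---|---|
| No | No | No | No |
| No | Yes | Yes | No |
| Yes | No | Yes | No |
| Yes | Yes | Yes | Yes |

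Section 9.1 states: "The study consists of Screening, Observation, Treatment, Extension, and Follow-up Phases". Section 9.2 adds: "The Follow-up Phase was set to be 70 days after the last dose of the study drug". If the study period includes follow-up, cover throughout it already includes the 70 days, and the third row cannot arise. Only the second row is then a wording fault.

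**Backstops.** Inclusion 10 asks for willingness to comply with the protocol, but it adds no contraception rule. No other section of the copy reviewed imposes one.

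**The case against.** **The gap is narrow.** On the stricter reading of *unprotected* only a small group escapes, and an investigator would probably notice a woman who refuses contraception. This stands as a limit on size, but it does not close the gap.

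**Exclusion 32 can be over-read.** A reader might infer that a couple could enter while planning contraception only after the last dose, leaving the whole dosing period uncovered, and might attach a percentage to that. The documents do not support this. The exemption requires a partner who is practising contraception when entry is decided, and the sperm-donation ban shows that both periods are intended. This is a wording repair only.

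**The reference to the criteria above in Exclusion 32.** A reader might infer that it is inverted, because the preceding bullets are exclusions. It makes sense if it points to the definition of non-childbearing status immediately before it, and the exemption's mention of partners not of childbearing potential fits that. It is no more than an ambiguity.

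**The copy reviewed is incomplete.** Consent pages were removed and may state a contraception duty. All sites are in Japan and non-English text was also removed, so the English may be a translation; that is an inference, not a stated fact. It weakens any point resting on a single *or* more than it weakens the structure of Exclusion 31.

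**It is too late for this trial.** Section 7 says the last subject entered the Extension Phase in March 2018, so no screening decision can change. This stands and determines what the fix can achieve.

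**Conclusion.** The concern holds for Exclusion 31 as a minor drafting fault in a safety criterion. Read as written, 1 of 12 logical profiles of a woman who declines all highly effective contraception is not excluded. Its frequency is unknown and probably low, and its width depends on the undefined word *unprotected*. The amendment log shows no change to Exclusions 31 or 32 in Versions 2 to 6, so the wording appears to have governed all screening. Nothing in the documents shows that such a woman was enrolled or that harm followed.

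The *or* in the Exclusion 32 exemption is a secondary wording point with clear intent. Alpha, power, the estimates and the primary analysis are not affected. The conclusion assumes that the English text reflects what sites used and that no contraception duty stands in the removed consent pages. Neither can be checked here.

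**What to change.** Reword in both the Synopsis and Section 9.3.2:

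1. **Exclusion 31:** exclude any woman of childbearing potential who does not agree to highly effective contraception throughout the study and until 70 days after the last dose, regardless of intercourse in the previous 30 days.
2. **Exclusions 31 and 32:** change the link between the two periods to *and until 70 days* in the three contraception bullets of 31 and in the exemption of 32. Changing 32 alone would leave mixed wording, and on a strict reading women who agree for only one period would escape 31. The sperm-donation ban already covers both periods and can stay.

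The first change excludes the one missed profile. The cost is the wording of two criteria in two places, with no effect on sample size, procedures or analysis. A stand-alone amendment is not worthwhile: under Section 5.1 it would need IRB review, at approximately 100 sites (Section 6), with enrolment already closed. Carry the wording into any later E6011 protocol that re-uses this text, where the added cost is close to nil.

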4 LIST OF ABBREVIATIONS AND DEFINITIONS OF TERMS

Abbreviation	Term
ACR	American College of Rheumatology
ADL	activities of daily living
ANCOVA	analysis of covariance
Ang2	angiopoietin 2
ALP	alkaline phosphatase
ALT	alanine aminotransferase (SGPT)
AST	aspartate aminotransferase (SGOT)
ATC	anatomical therapeutic chemical
BUN	blood urea nitrogen
CCP	cyclic citrullinated peptide
CDAI	clinical disease activity index
CH50	50% hemolytic unit of complement
CRA	clinical research associate
CRO	contract research organization
CRP	C-reactive protein
CTCAE	common terminology criteria for adverse events
CX3CR1	CX3C motif chemokine receptor 1 (receptor of fractalkine)
DAS	disease activity score
DNA	deoxyribonucleic acid
DMARDs	disease-modifying antirheumatic drugs
EGF	epidermal growth factor
ESR	erythrocyte sedimentation rate
EULAR	European League Against Rheumatism
FAS	full analysis set
FKN	fractalkine
γ-GTP	γ-glutamine transpeptidase
GCP	good clinical practice
GM-CSF	granulocyte macrophage colony-stimulating factor
HAQ	health assessment questionnaire
HbA1c	hemoglobin A1c
HBc	hepatitis B virus core
HBs	hepatitis B virus surface
HBV	hepatitis B virus
HCV	hepatitis C virus
HIV	human immunodeficiency virus
HTLV-1	human T cell lymphotropic virus-1
ICAM-1	intercellular adhesion molecule-1
ICH	International Conference on Harmonisation

Abbreviation	Term
IFN- γ	interferon- γ
IgG	immunoglobulin G
IL	interleukin
IVRS/IWRS	interactive voice/web response systems
LDH	lactate dehydrogenase
LRG1	leucine-rich alpha-2 glycoprotein 1
MedDRA	Medical Dictionary for Regulatory Activities
MMP	matrix metalloproteinase
MRI	magnetic resonance imaging system
mTSS	modified total sharp score
MTX	methotrexate
NSAIDs	nonsteroidal antiinflammatory drug
PD	pharmacodynamics
PK	pharmacokinetics
PML	progressive multifocal leukoencephalopathy
PPS	per protocol set
PT	preferred term
QOL	quality of life
QTcF	QT interval corrected for heart rate using Fridericia's formula
RA	rheumatoid arthritis
RF	rheumatoid factor
SAA	serum amyloid A
SDAI	simple disease activity index
SOC	system organ class
SOP	standard operating procedures
TEAE	treatment emergent adverse events
TNF α	tumor necrosis factor α
TNF-RI	tumor necrosis factor receptor-I
TRACP-5b	tartrate resistant acid phosphatase 5b
VAS	visual analog scale
VCAM-1	vascular cell adhesion molecule-1
VEGF	vascular endothelial growth factor
WHO DD	World Health Organization Drug Dictionary

5 ETHICS

5.1 Institutional Review Boards/Independent Ethics Committees

The protocol, informed consent form (ICF), and appropriate related documents must be reviewed and approved by an Institutional Review Board (IRB) constituted and functioning in accordance with Good Clinical Practice (GCP). Any protocol amendment or revision to the ICF will be resubmitted to the IRB for review and approval, except for changes involving only logistical or administrative aspects of the study (eg, change in CRA[s], change of telephone number[s]). Documentation of IRB compliance with the GCP regarding constitution and review conduct will be provided to the sponsor.

A signed letter of study approval from the IRB chairman must be sent to the head of the medical institution before study start and such documents must be sent to the sponsor before the release of any study drug to the site by the sponsor or its designee. If the IRB decides to suspend or terminate the study, the head of the medical institution will immediately send the notice of study suspension or termination to the sponsor.

In accordance with GCP, study progress is to be reported to IRB annually (or as required) by the investigator via the head of the medical institution. The sponsor will submit periodic reports and inform the IRB via the investigator and the head of the medical institution of any reportable adverse events (AEs) per GCP and local IRB standard operating procedures. Upon completion of the study, the investigator will provide the IRB and the sponsor with a brief report of the outcome of the study via the head of the medical institution.

5.2 Ethical Conduct of the Study

This study will be conducted in accordance with standard operating procedures of the sponsor (or designee), which are designed to ensure adherence to the following:

- Principles of the World Medical Association Declaration of Helsinki (Ethical Principles for Medical Research Involving Human Subjects)
- GCP
- Article 14, Paragraph 3, and Article 80-2 of the Pharmaceutical Affairs Law (Law No. 145, 1960)

5.3 Subject Information and Informed Consent

As part of administering the informed consent document, the investigator or subinvestigator must explain to each subject (or guardian/legally acceptable representative) the nature of the study, its purpose, the procedures involved, the expected duration, the potential clinical risks and benefits involved, any potential discomfort, potential alternative procedure(s) or course(s) of treatment available to the subject, and the extent of maintaining confidentiality of the subject's records. Each subject must be informed that participation in the study is voluntary, that he/she may reject the participation or withdraw from the study at any time, and that the rejection or withdrawal of consent will not affect his/her subsequent medical treatment or relationship with the treating physician.

This informed consent should be given by means of a standard written statement, written in nontechnical language. The subject (or the subject's legally acceptable representative) should understand the statement before signing and dating it and will be given a copy of the signed document. The subject will be asked to sign an ICF before any study-specific procedures are performed. No subject can enter the study before his/her informed consent has been obtained.

An unsigned copy of an IRB-approved ICF must be prepared in accordance with GCP and all applicable local regulations. Each subject must sign an approved ICF before study participation. The form must be signed and dated by the investigator or subinvestigator (and clinical research coordinator, if required). The original, signed ICF for each subject will be verified by the sponsor and kept on file according to local procedures at the site. The subject (or the subject's legally acceptable representative) should be informed in a timely manner if new information becomes available that may be relevant to the subject's willingness to continue participation in the study. The communication of this information should be documented.

6 INVESTIGATORS AND STUDY PERSONNEL

This study will be conducted by qualified investigators selected by the sponsor (Eisai) at approximately 100 investigational sites in Japan.

The name and telephone and fax numbers of the medical monitor and other contact personnel at the sponsor are listed in Appendix 2.

7 INTRODUCTION

Rheumatoid arthritis (RA) is an autoimmune disease characterized by the inflammation of synovium in a joint. Its major clinical symptoms are pain and swelling of joints of limbs. Progressed inflammation of synovium causes joint destruction, which leads to impaired activity of daily living (ADL) and eventually lowers quality of life (QOL). Joint dysfunction may be reversible after treatment in many cases at the onset, but it often becomes irreversible after the development of joint destruction. In addition, prolonged disease increases the incidence of complications such as interstitial pneumonia and secondary amyloidosis. As a result, RA patients are considered to have a shorter life expectancy than healthy adult people by approximately 10 years due to events including cardiovascular system associated with infection and inflammation as well as dysfunction caused by joint destruction ([Tanaka Y, 2011; Miyasaka N, 2013](#)).

Estimated prevalence of RA is approximately 1% of the world population, of which 600,000 to 700,000 are Japanese. Patients most commonly affected are women in their 40s to 50s, who are in their most productive years. This causes significant psychological, social, and financial burdens to their family in addition to their own physical difficulties ([Ochi T, et al., 2004](#)).

Disease-modifying antirheumatic drugs (DMARDs) have been mainly used to treat RA patients, with methotrexate (MTX) being the standard medication. However, some patients

do not sufficiently benefit from DMARD therapy as they experience adverse reactions, or do not adequately respond to DMARDs (Kremer JM, 2001).

There are several reports indicate that the emergence of biologics such as anti-TNF agents can improve clinical symptoms, prevent joint destruction progression, and improve impaired physical function in patients who do not adequately respond to DMARD therapy (Maini R, et al., 1999; Nishimoto N, et al., 2007; Takeuchi T, et al., 2013). Meanwhile, the remission rate is approximately 20% to 40% after biologics treatment (Takeuchi T, 2010) and there are patients who are unable to continue the treatment due to the adverse reactions. Thus, medical needs are not fully satisfied and development of highly effective and safer drugs with a new mechanism of action is eagerly anticipated.

E6011 is the world's first humanized fractalkine (FKN) monoclonal antibody (mAb). The antibody was created in KAN Research Institute, Inc., a research subsidiary of Eisai Co., Ltd. FKN is thought to have both chemotaxis and adhesive effects to leukocytes and to play an important role on cell invasions in inflamed tissues (Imai T, et al., 2005). E6011 inhibited human FKN-induced chemotaxis of human fractalkine receptor (CX3CR1) expressing mouse B lymphocyte precursor cells, in vitro. In a collagen-induced arthritis (CIA) model in mice, a widely used animal model for RA, administrations of FKN monoclonal antibodies against mouse FKN showed amelioration of the status of RA. CX3CR1 and FKN are reported to be strongly expressed in the synovium of patients with RA (Nanki T, et al., 2002) and the relationship with RA is suggested. FKN is reported to be involved in the differentiation of osteoclast (Koizumi K, et al., 2009); thus, E6011 is also expected to have an inhibitory effect against the structural damage of joints through inhibition of bone absorption in RA.

A Phase 1 clinical study of single intravenous (IV) administration of E6011 in healthy adults (E6011-J081-001, hereinafter called Study 001) and a Phase 1 clinical study of single subcutaneous (SC) administration of E6011 in healthy adults (E6011-J081-002, hereinafter called Study 002) have been completed. In Study 001 (IV: 0.0006 to 10 mg/kg) and Study 002 (SC: 50 to 400 mg), adverse events which could affect safety and tolerability have not been observed in any dose group.

In a Phase 1/2 clinical study of repeated subcutaneous administrations of E6011 in RA subjects (E6011-J081-103, hereinafter called Study 103), we evaluated the safety and tolerability of E6011 at repeated subcutaneous administrations of 100 mg, 200 mg, and 400 mg as primary objective. Analysis of 12-week dosing presented no concerns about the safety and tolerability in RA subjects who repeatedly received E6011 at 100 to 400 mg and the clinical symptoms of RA tended to be improved in exploratory efficacy evaluations. In consideration of current situation where an RA medication with novel mechanism of action in terms of safety and efficacy is desired and E6011 is highly expected to provide benefits to RA patients as a novel therapeutic agent, a double-blind, placebo-controlled, parallel-group comparison study was planned to assess the dose response of the efficacy and safety of E6011.

The last subject entered the Extension Phase (open-label) in March 2018, and all subjects had completed 52 weeks of treatment with E6011 by March 2019. Consequently, it was

considered unnecessary to conduct any non-safety assessments after March 2019, and the protocol will be revised to Version 6.

